6. STUDY DRUG ADMINISTRATION

6.1. Description of Study Drug Administration

IMGC936 is administered by IV infusion. The drug product is diluted in a solution of sterile Dextrose 5% in Water (D5W) in an IV bag for administration with an infusion pump.

For Schedule A, IMGC936 is administered on Day 1 of each 21-day cycle.

For Schedule B, IMGC936 is administered on Day 1, Day 8, and Day 15 of a 28-day cycle for Cycles 1 and 2. For each subsequent 28-day cycle (Cycle 3 and beyond), IMGC936 is administered on Day 1 and Day 8. Subsequent cycles may be delayed up to 3 days after the previous cycle for scheduling purposes. IMGC936 is administered as an IV infusion at the assigned dose for each cohort, over approximately 2 to 3 hours.

6.2. Method of Assigning Participants to Study Drug

Participants will be assigned sequentially to dose-escalation cohorts as specified in Section 4.1.1.

6.3. Blinding

This is an open-label study.

6.4. Emergency Unblinding

Not applicable. This is an open-label study.

6.5. Guidelines for Discontinuation of Participant from Study

Participants who are no longer on study drug but are still followed on the study can be terminated from the study for the following reasons:

- Completion of protocol-defined follow-up period
- Uncontrolled intercurrent illness unrelated to cancer that prevents continuing study follow-up
- Noncompliance with protocol-required evaluations
- The participant requests to be discontinued from the study, ie, withdrawal of consent
- The sponsor, investigator, or regulatory agency terminates the study
- Death

6.6. Study Drug and Supplies

6.6.1. IMGC936

IMGC936 drug product is a sterile and preservative-free solution. The drug product yields a solution that is clear to slightly opalescent, colorless to pale yellow, and essentially free from foreign visible particles. It is supplied at a nominal protein concentration of 7 mg/mL in a single-dose glass vial containing 100 mg/14.3 mL IMGC936. The drug product is formulated in a

solution of 1.18 mg/mL succinic acid, 0.35 mg/mL sodium hydroxide, 90 mg/mL sucrose, and 0.1 mg/mL polysorbate 20, pH 4.7. The concentration and function of each component in IMGC936 drug product are summarized in Table 5.

Table 5: IMGC936 Drug Product Composition

Name of Ingredient	Concentration (mg/mL)	Amount per Vial (mg) ^a	Function ^b
IMGC936	7	100	Active ingredient
Succinic acid	1.18	16.90	Buffer component
Sodium hydroxide	0.35	5.00	Buffer component
Sucrose	90	128.70	Stabilizer
Polysorbate 20	0.10	1.40	Surfactant

^a Amount per vial based on 14.3 mL nominal fill volume.

6.7. Study Drug Infusion Preparation

6.7.1. General Guidelines and Precautions

Under no circumstances is the investigator allowed to release clinical study supplies for use by another physician not named on Form FDA (Food and Drug Administration) 1572 (or equivalent form) or to administer study drug to patients not enrolled in this study. Study drug must be dispensed at an institution specified on Form FDA 1572 (or equivalent form).

6.7.1.1. IMGC936 Dosage

The calculated dose of IMGC936 will be administered based on the participant's body weight at Cycle 1, Day 1. Body weight will be measured at screening and Day 1 of each cycle. Significant ($\geq 10\%$) change in body weight from baseline should prompt recalculation of dose. Refer to the pharmacy manual for further instructions on allowable parameters for dose rounding.

IMGC936 should not be administered as an IV push or bolus. All doses of IMGC936 will be diluted in D5W and administered as an IV infusion with a commercially available infusion pump. All infusion pumps must be calibrated in accordance with the institutional standards, policies, and procedures to ensure consistent, accurate delivery of IMGC936.

Infusion or allergic reactions may occur with the infusion of mAb and other protein-based therapeutics. Precautions for anaphylaxis should be observed during administration. Refer to Section 7.1 for specific guidelines regarding the management of infusion reactions. Supportive care measures consistent with optimal care will be provided throughout the study according to institutional standards.

6.7.2. Study Drug Preparation and Administration

Visually inspect parenteral drug products for particulate matter and discoloration prior to administration. Return the vial if the solution is cloudy, there is pronounced discoloration (solution may have pale-yellow color), or there is foreign particulate matter.

^b Excipients are added to Water for Injection (United States Pharmacopeia).

Instructions on study drug preparation for IV infusion are detailed in the pharmacy manual.

Do not mix the study drug with, or administer as an infusion with, other medicinal products or IV fluids other than D5W.

IMGC936 is administered as an IV infusion following preparation instructions as outlined in the pharmacy manual. Details on required compatible infusion materials and IV infusion instructions are included in the IV infusion instructions manual.

All doses of IMGC936 must be diluted in sterile D5W prior to dose administration. IMGC936 diluted in D5W must be within the concentration range of 0.4 mg/mL to 6.0 mg/mL for IV administration. See the pharmacy manual for instruction on dilutional volumes for each dose level. Administer the prepared diluted IMGC936 through an IV line with a commercially available infusion pump. A sterile, non-pyrogenic, low protein binding polyethersufone (PES) 0.2 or 0.22 μ m in-line IV filter must be used for IV administration of IMGC936. Do not administer as an IV push or bolus.

IMGC936 should be administered at a flat infusion rate of 80 mL/hr at any treatment cycle. Recommended adjustments in infusion rate are outlined in the IV infusion instructions manual should an infusion reaction occur, or a dose change be required. After infusion, the IV line will be flushed with D5W to ensure delivery of the full dose. Additional directions in the pharmacy manual and IV infusion instructions should be used should there be any subsequent changes to the preparation of IMGC936 or its IV administration.

Because there is no preservative in the study drug vial, study drug administration should begin immediately after the study drug is prepared, but no later than 4 hours when the diluted IMGC936 IV bag is stored at room temperature after preparation. Although, the diluted IMGC936 in the IV bag may be stored for up to 24 hours at 2°C to 8°C, it may not be used if the refrigerated storage time and expected administration time exceeds 24 hours. If the dose solution is stored at 2 to 8°C, it should be removed from the refrigerator at least 30 to 60 minutes prior to administration, to allow solution to reach room temperature.

Participants will be carefully observed during each infusion and vital signs are taken as outlined in Appendix 1. Participants will remain in the clinic under observation for 4 hours after the first infusion, and for at least 1 hour after each subsequent infusion. While in the treatment area, participants are closely monitored for AEs.

6.8. Study Drug Compliance

The study drug will be administered by healthcare professionals under the supervision of the investigator or designee. Records of dose calculation, administration, and dosing regimen will be accurately maintained by site staff. The sponsor or its designee will monitor and review dose calculation, administration, and regimen as well as medication accountability per the study monitoring plan.

6.9. Packaging and Labeling

IMGC936 drug product is filled into Type I, 20 mL clear glass vials. Each vial is stoppered with a 20 mm diameter butyl rubber stopper that has an ethylene tetrafluoroethylene (ETFE) fluoropolymer coating on the product contact surface and on the top of the stopper. The

stoppered vial is sealed with non-embossed 20 mm overseal with a plastic overseal and an aluminum collar.

IMGC936 is labeled according to local regulatory health authority requirements. Please see the pharmacy manual for detailed information about the packaging of the study drug. All study drug will be labelled with a minimum of the protocol number, directions for use, and storage conditions; the statements "For clinical trial use only," and/or "CAUTION: New Drug – Limited by Federal (United States) Law for Investigational Use"; and the sponsor's name and address.

6.10. Study Drug Accountability

The investigator or their designee is required to maintain accurate drug accountability records. Instructions and the required accountability documentation will be provided to the investigator or their designee. When the study is completed, copies of study drug accountability records must be sent to the sponsor. The original drug accountability records must be maintained with the rest of the documentation in accordance with Section 15.1 of the protocol.

Accurate accounting of all study medication must be maintained. The investigator agrees to keep an inventory of study drugs using the institution's drug accountability logs or logs provided by the sponsor. Drug disposition records must be kept in compliance with applicable guidelines and regulations.

A pharmacy manual will be provided to the investigator or designee. Additional details regarding storage, handling, and accountability can be found in the pharmacy manual.

6.10.1. IMGC936

Vials containing study drug should be stored upright under refrigeration at 2°C to 8°C (36°F to 46°F) in an appropriate, locked room accessible only to pharmacy personnel, the investigator, or duly designated personnel. To ensure compliance with storage conditions, temperature logs should be maintained. Vials should be protected from light during storage by storing the vial in the original carton. Vials should not be shaken or frozen. Standard laboratory practices should be used for avoidance of contact with IMGC936.

6.11. Investigational Product Disposition at End of Study

Upon completion or termination of the study, all unopened vials of study drug will either be disposed of at the study site according to the study site's standard operating procedure or returned to the sponsor, as determined by the study site. The sponsor must evaluate and approve the study site's standard operating procedure for drug disposal prior to initiation of drug destruction by the site. If the study site chooses to destroy study drug, the investigator must ensure arrangements are made for proper disposal and that appropriate records of disposal are documented and maintained, and copies provided to the sponsor. All drug returns to the sponsor or its representative must be accompanied by the appropriate documentation.

7. POTENTIAL ADVERSE EVENTS AND SUPPORTIVE CARE MEASURES

7.1. Infusion Related Reactions

Infusion-related reactions (IRRs) (non-serious and serious) are adverse events of special interest (AESI) and must be reported using an SAE form per Section 12.2.2.

The IRRs associated with administration of mAb-based therapeutics should be managed according to the standard practice of medicine. General guidelines for management of such reactions are provided in this section. However, severe reactions may require more intensive interventions (eg, steroids).

Participants should be monitored closely for development of IRRs during infusions. Medications and supportive measures for treatment of severe hypersensitivity reactions should be available for immediate use for an infusion reaction during study drug administration and may include, but are not limited to, subcutaneous epinephrine (0.3 to 0.5 mL of a 1:1000 solution), antihistamines (eg, diphenhydramine 25 to 50 mg IV [or orally (PO) if IV not available]), corticosteroids (eg, hydrocortisone 20 to 40 mg IV push or equivalent), IV fluids, vasopressors, oxygen, bronchodilators, and antipyretics. Resuscitation equipment and other supplies for the emergency management of an allergic/toxic reaction must be available. The participant should be treated according to the best available local practices and procedures. All supportive measures consistent with optimal care will be provided throughout the study according to institutional standards.

Should symptoms of fever, rigors, or chills develop, it may be difficult to distinguish among potential causes of the symptoms including emerging infection or infusion reaction. Participants should be evaluated carefully for the presence of infection (including COVID-19), with the acquisition of cultures and/or implementation of empiric antibiotic therapy as appropriate based on the assessment of the investigator. Refer to Section 7.1.3 for guidance on the management of IRRs.

Participants who experience a Grade 2 or greater IRR following administration of IMGC936 will have blood drawn to further study the IRR, including determination of drug concentration and antibodies to IMGC936. Samples should be obtained within 3 hours of the onset of the reaction and again 1 week later.

7.1.1. Grading and Management of Infusion Reactions

Infusion reactions are graded per the criteria in Table 6.

Table 6: Grading of Infusion Related Reactions (CTCAE v5.0)

System Organ Class	Injury, Poisoning and Procedural Complications	Immune System Disorders
Preferred Term	Infusion Related Reaction	Allergic Reaction
Grade 1	Mild transient reaction; infusion interruption not indicated; intervention not indicated	Systemic intervention not indicated
Grade 2	Therapy or infusion interruption indicated but responds promptly to symptomatic treatment (eg, antihistamines, non-steroidal anti-inflammatory drugs, narcotics, IV fluids); prophylactic medications indicated for ≤ 24 hours	Oral intervention indicated
Grade 3	Prolonged (eg, not rapidly responsive to symptomatic medication and/or brief interruption of infusion); recurrence of symptoms following initial improvement; hospitalization indicated for clinical sequelae	Bronchospasm; hospitalization indicated for clinical sequelae; IV intervention indicated
Grade 4	Life-threatening consequences; urgent intervention indicated	
Grade 5	Death due to AE	

Abbreviations: AE: adverse event; CTCAE: Common Terminology Criteria for Adverse Events; IV: intravenous.

7.1.2. Premedication and Prophylaxis

Premedication is required to mitigate the occurrence of infusion reactions. Equivalent medications may be substituted based on institutional standard of care and availability. Oral premedication should be given at least 30 minutes prior to infusion of study drug include:

- Acetaminophen 650 to 1000 mg PO, or ibuprofen 400 mg PO
- Diphenhydramine 25 to 50 mg IV (or PO if IV is not available) or equivalent H1 antagonist

No prophylactic pre-infusion steroid administration is required.

For subsequent study drug administration in a participant who had an IRR that was not adequately or only moderately controlled with acetaminophen and diphenhydramine, IV corticosteroids should be considered as part of the premedication regimen, (eg, 10 mg dexamethasone or equivalent. Nonsteroidal premedications may be administered prior to the subsequent infusion, if warranted.

IMGC936 ImmunoGen, Inc Clinical Study Protocol: IMGC936-0901 Amendment 3 29 March 2022

7.1.3. Management of Observed Infusion Reactions

All changes in the study drug infusion, including interruption of the infusion and its duration as well as reductions in infusion rate and duration, must be recorded. The following are treatment guidelines (which may be modified as needed by the investigator according to the best practices of medicine) for IRR. Note that for participants who have an infusion reaction requiring corticosteroid administration, corticosteroid administration should be used as prophylaxis on subsequent infusions.

Grade 1:

- Slow the infusion rate by 50%.
- Monitor the participant for worsening of condition.
- Continue rate at 50% reduction and increase dose rate to the original rate by doubling the infusion rate after 30 minutes, as tolerated to the initial rate. Consideration can be given to beginning subsequent infusions at 50% rate and increasing as tolerated.
- If a participant has an infusion reaction, prophylactic pre-infusion medications should be given prior to all subsequent infusions. The following prophylactic pre- infusion medications are recommended prior to future study drug infusions for participants who experience Grade 1 infusion reactions: diphenhydramine 25 to 50 mg (or equivalent) IV (or PO if IV not available) and acetaminophen 650 mg PO and/or ibuprofen 400 mg PO, with or without famotidine 40 mg PO or 20 mg IV (or equivalent H2 antagonist) at least 30 minutes before additional study drug administrations.
- Report the event as an AESI.

Grade 2:

- Stop the infusion.
- Administer diphenhydramine hydrochloride 25 to 50 mg IV (or PO if IV not available).
- Acetaminophen 650 mg PO or ibuprofen 400 mg PO for fever.
- Oxygen and bronchodilators for mild bronchospasm.
- Resume the infusion at 50% of the prior rate once the infusion reaction has resolved or decreased to Grade 1. The rate may then be escalated to the original rate after 30 minutes, as tolerated. Consideration can be given to beginning all subsequent infusions at 50% rate and increasing as tolerated.
- Monitor for worsening condition. If symptoms recur, discontinue the infusion; no further study drug will be administered at that visit.
- Prophylactic pre-infusion medications should be given prior to subsequent study drug infusions. Participants who experience a Grade 2 infusion reaction, for subsequent doses of study drug, pre medicate with diphenhydramine hydrochloride 25 to 50 mg IV (or PO if IV is not available), acetaminophen 650 mg PO and/or ibuprofen 400 mg

PO, with or without famotidine 40 mg PO or 20 mg IV (or equivalent H2 antagonist) at least 30 minutes before additional study drug administrations. For these participants, corticosteroids (dexamethasone 10 mg IV or hydrocortisone 25 to 100 mg IV or higher) also should be added to the premedication regimen for subsequent dosing of study drug.

Report the event as an AESI.

Grade 3:

- Stop the infusion and disconnect the infusion tubing from the participant.
- To avoid exacerbation of infusion reaction: do not flush the tubing aspirate residual drug from the vascular access device.
- Administer diphenhydramine hydrochloride 25 to 50 mg IV (or PO if IV is not available), dexamethasone 20 mg IV (or equivalent), and other medications/treatment as medically indicated. Higher doses of corticosteroids (eg, methylprednisolone 2 to 4 mg/kg IV or the equivalent) may also be considered for acute management.
- IV fluids, supplemental oxygen, and bronchodilators should be considered, as appropriate.
- If the Grade 3 infusion reaction occurs with study drug administration, it will be discontinued for that day. If symptoms have resolved to baseline within 12 hours, study drug may be infused the next day. In addition, participants should be pre medicated for this re-challenge and for any subsequent doses of study drug with the following: diphenhydramine hydrochloride 25 to 50 mg IV (or PO if IV is not available), acetaminophen 650 mg PO and/or ibuprofen 400 mg PO, with or without famotidine 40 mg PO or 20 mg IV (or equivalent H2 antagonist). Corticosteroids (dexamethasone 10 to 20 mg IV or hydrocortisone 50 to 100 mg IV or higher) should be considered as well.
- Participants who have a Grade 3 infusion reaction that does not resolve within 12 hours despite medical management should not receive further study drug. Participants who experience a second Grade 3 infusion reaction at the time of study drug re-challenge will permanently discontinue study drug.
- Report the event as an AESI and as an SAE, if appropriate.

Grade 4:

- Stop the infusion and disconnect the infusion tubing from the participant.
- To avoid exacerbation of infusion reaction: do not flush the tubing aspirate residual drug from the vascular access device.
- Administer diphenhydramine hydrochloride 50 mg IV (or PO if IV is not available), dexamethasone 20 mg IV (or more as considered appropriate), and other medications/treatment as medically indicated.
- Give epinephrine or bronchodilators as indicated.

IMGC936 ImmunoGen, Inc Clinical Study Protocol: IMGC936-0901 Amendment 3 29 March 2022

- Support ventilation and blood pressure as indicated.
- Report the event as an AESI and an SAE.
- Participants who have a Grade 4 infusion reaction will not receive further study drug.

Grade 5:

• Report the event as an AESI and an SAE.

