4.3. Expansion Phase Safety Monitoring

Safety will be evaluated continuously and in aggregate in the expansion cohorts. Safety assessments will be based on all TEAEs and abnormal laboratory values. If at any time \geq 33% of at least 3 participants who received study drug in an expansion cohort experience a study drug—related TEAE leading to discontinuation, enrollment will be paused within that cohort and may also be paused in ongoing cohorts at the discretion of the sponsor. If it is determined that the clinical investigation should be halted due to an unacceptable participant risk, the study must be terminated after appropriate consultation between the sponsor and investigators.

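### Section 7.1.3 gives two steroid premedication instructions of different strength for the same Grade 3 participant at re-challenge

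*Protocol*

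**What the plan says.** Four places in the protocol address steroid premedication after an infusion-related reaction.

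- Section 7.1.2, general rule, for a reaction that acetaminophen and diphenhydramine did not control well: "IV corticosteroids should be considered as part of the premedication regimen".
- Section 7.1.3, opening note, not limited by grade: "Note that for participants who have an infusion reaction requiring corticosteroid administration, corticosteroid administration should be used as prophylaxis on subsequent infusions".
- Section 7.1.3, Grade 2 block: corticosteroids "also should be added to the premedication regimen for subsequent dosing of study drug".
- Section 7.1.3, Grade 3 block, for the re-challenge and any later dose: "Corticosteroids (dexamethasone 10 to 20 mg IV or hydrocortisone 50 to 100 mg IV or higher) should be considered as well".

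The acute steps of the Grade 3 block tell the site to give "dexamethasone 20 mg IV (or equivalent), and other medications/treatment as medically indicated". On re-challenge the block says: "If symptoms have resolved to baseline within 12 hours, study drug may be infused the next day". A second Grade 3 reaction at re-challenge means permanent discontinuation. Grade 4 participants receive no further study drug, so Grade 3 is the highest grade at which re-challenge can occur. The section describes its steps as guidelines that the investigator may modify.

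**The concern.** The opening note and the Grade 3 block govern the same participant and the same infusions but differ in how firmly they call for a steroid. The Grade 3 block is also less firm than the Grade 2 block. Table 6 describes Grade 2 as a reaction that settles promptly with symptomatic treatment and Grade 3 as a prolonged or recurring one. The documents give no reason for the softer instruction at the higher grade.

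The study plans about 26 centers, so different readings are realistic. Section 8.1.1 adds to the uncertainty. It asks sites to limit corticosteroids except where the protocol specifies them, and leaves open whether an instruction to consider a steroid counts as specifying one.

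The direct stake is the safety of a participant re-infused soon after a severe reaction. A possible further effect is on drug-related events leading to discontinuation. These are part of a secondary endpoint in expansion (Section 3.2.2) and drive the enrollment pause in Section 4.3.

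**Working it through.** The check is mainly textual, because the plan states no figure on this point.

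1. **Does the opening note reach Grade 3?** It applies to any reaction that required a corticosteroid. The Grade 3 acute steps list dexamethasone as something to give, not as an option. A Grade 3 reaction managed as written therefore falls under the note.

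2. **Do the two instructions cover the same infusions?** The note covers subsequent infusions. The Grade 3 block covers the re-challenge and any later dose. These are the same infusions.

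3. **Strength of the instruction, by grade:**

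| Source | Steroid in later premedication |
|---|---|
| Grade 1 block | Not listed |
| Grade 2 block | To be added |
| Grade 3 block | To be considered |
| Opening note, applied to Grade 3 | To be used |

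The obligation rises from Grade 1 to Grade 2 and falls from Grade 2 to Grade 3. At Grade 3 it is below the note that covers the same participant.

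4. **Dose.** After Grade 2 the listed doses are dexamethasone 10 mg, or hydrocortisone 25 to 100 mg or higher. After Grade 3 they are dexamethasone 10 to 20 mg, or hydrocortisone 50 to 100 mg or higher. The Grade 3 doses are equal or higher, so only the obligation is weaker.

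5. **Which outcomes could move?** Protocol Section 14.5.1 counts participants with an event, and SAP Section 7.2 counts a repeated event once, at its worst grade. A Grade 3 participant is already counted, at Grade 3, before any re-challenge. Steroid use at re-challenge cannot change how many participants have a reaction. It changes the maximum grade only if the repeat reaction is worse. It could change whether the participant discontinues.

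6. **Where does this apply?** Section 4.2.2 makes any non-hematologic event of Grade 3 or higher a DLT and does not list infusion reactions among its exclusions. Section 5.4 lists a DLT in the escalation window as a reason to stop study drug. The window is 21 days on Schedule A and 28 days on Schedule B, where it spans the Day 1, 8 and 15 infusions. The Grade 3 re-challenge text in 7.1.3 makes no exception for that window, so it also needs reconciling with 4.2.2 and 5.4. If 5.4 governs there, the steroid conflict matters mainly in later cycles and in expansion.

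7. **Pause rule in Section 4.3.** The threshold is 33% or more of at least 3 treated participants. With 3 treated, one discontinuation gives 1/3 = 33.3% and meets it. With 13 treated, four give 4/13 = 30.8% and do not, while five give 5/13 = 38.5% and do. This holds for any drug-related discontinuation, whatever its cause.

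**The case against.** The strongest reply is that 7.1.3 is guidance the investigator may modify, so discretion over steroids is intended and uniform verbs would still leave the choice to the investigator. The point about discretion stands, and it means this is inconsistent guidance rather than a clash of absolute rules. But freedom to depart from guidance does not settle what the guidance is when two of its lines disagree for the same participant and infusion.

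A second reply is that the specific Grade 3 block overrides the general note. The protocol does not say so. Because Grade 4 participants are not re-dosed and the Grade 1 and Grade 2 acute steps list no steroid, Grade 3 is the main group the note can reach. Letting the block override it would leave the note with little to do.

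A third reply concerns 7.1.2 and the Grade 2 block, which a reader might take as a second full contradiction. The documents do not support that. Section 7.1.2 is triggered by poor control and the Grade 2 block by grade, so they overlap only in part, and a general rule to consider can sit beside a more specific rule to add. Aligning them is tidying, and the Grade 3 conflict stands without it.

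**Conclusion.** The point holds as an internal inconsistency: two instructions of different strength for steroid premedication at Grade 3 re-challenge and later doses, with the Grade 3 block also less binding than the Grade 2 block. It should be corrected because it bears on safety at a re-challenge that may come the next day. It may also bear on drug-related discontinuations, mainly in expansion and after the DLT window.

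Three stronger readings are tempting, and the documents do not support them. A reader might infer that infusion-reaction incidence, the only adverse event of special interest, becomes non-comparable across dose levels and cohorts; under the counting rules above it does not. A reader might infer that treatment weakens as severity rises; the dose does not fall, and the obligation falls at one step only. A reader might take the Section 4.3 rule ("enrollment will be paused within that cohort") as the size of the problem; one discontinuation in three would trigger it for any drug-related cause, so it says nothing about the effect of this wording.

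No effect size can be given, because the documents state no repeat-reaction rate with or without steroid. The conclusion assumes that a Grade 3 reaction managed with the listed dexamethasone counts as one requiring corticosteroid under the opening note.

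**What to change.** Reconcile the opening note of 7.1.3 with its Grade 2 and Grade 3 blocks so that each grade carries one steroid premedication instruction for re-challenge and later infusions, and remove the conflicting wording. Align the general sentence in 7.1.2 with the result. State how the Grade 3 re-challenge text relates to 4.2.2 and 5.4 during the escalation DLT window. Which instruction applies at each grade is for the sponsor's clinicians.

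The cost is protocol wording only. Sample size, endpoints and the SAP analyses do not change.
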